# CIP339 Clinical Investigation Plan

D00456959

Version F

Page 60 of 93

Medtronic

 
sensor needle removal
 
• Residual redness associated with adhesive and/ or tapes
 
• Scarring
 
• Scab
 
• Blister
 
• Itchiness
 
• Inflammation
 
• Anxiety
 
• Incorrect sensor glucose reading results in incorrect diabetes management
 
• Subject over-treating secondary to alarms which can result in hyperglycemia or hypoglycemia
 
• Anxiety associated with insertion
 
	

Risks with Transmitter
 
Risks with transmitter may include:
 
 
• Skin irritation or reaction to adhesives
 
• Bruising
 
• Discomfort
 
• Redness
 
• Pain
 
• Rash
 
• Infection
 
• Irritation from tapes used with glucose-sensing products
 
• Raised bump
 
• Allergic reaction
 
• Soreness or tenderness
 
• Residual redness associated with adhesive and/ or tapes
 
• Scarring
 
• Scab
 
• Blister
 
• Itchiness
 
• Inflammation
 
	
Prevention and Mitigation
 
Prevention and mitigation include:
 
 
• Follow the provided user guides.
 
• Train on the proper use of the transmitters.
 

Risks with Serter
 
Risks with serters may include:
 
 
• Improper insertion may lead to device performance issue or hyperglycemia
 
	
Prevention and Mitigation
 
Prevention and mitigation include:
 
 
• Follow the provided user guides for insertions and care of device.
 
• Train on the proper use of the serter and skin preparation prior to insertion.
 

Risks with Fingersticks
 
Risks with frequent fingerstick testing may include:
	
Prevention and Mitigation
 
Prevention and mitigation include:
 
 
• Follow the provided user guides for use of the study meter with fingerstick testing.
 

*Medtronic Business Restricted*

**CONFIDENTIAL**

056-F275, vC Clinical Investigation Plan Template

 
Potential risks associated with frequent meter testing of blood glucose and blood ketones include discomfort and ecchymosis at tips of fingers
 
Potential risks associated with fingerstick testing include discomfort and bruising
 
	
 
Train on the proper use of the study meter and fingerstick testing.
 


Risk with Closed Loop Therapy with Meal Gesture Dosing
 
The risks associated with using the insulin pump in closed loop mode with meal gesture dosing are related to the potential for delivery of too much or too little insulin which can result in:
 
 
Hypoglycemia
 
Severe hypoglycemia
 
Hyperglycemia
 
Diabetic ketoacidosis
 
User entry error 
 
Patient entering false glucose values for any reason leading to hypoglycemia and hyperglycemia
 
Patient entering false BG values for calibration leading to hypoglycemia or hyperglycemia
 
 
 
Sensor failure resulting from patient failure to calibrate leading to hypoglycemia or hyperglycemia
 
Sensor over-reading resulting in hypoglycemia
 
Sensor under-reading resulting in hyperglycemia
 
Sensor missed transmission, or any other fault resulting in no SG value, leading to hyperglycemia or hypoglycemia
 
Voluntary insulin delivery (with the pump or with a syringe) immediately prior to entering Auto Mode may result in severe hypoglycemia despite shutting down insulin delivery by the algorithm
 
Hypoglycemia related to patient taking insulin via injection while in Closed Loop (Auto Mode)
 
Hypoglycemia or hyperglycemia related to entering or exiting Closed Loop (Auto Mode)
 
Insulin over-delivery due to potential interference from acetaminophen
 
Cyber security hacking into pump
 
	
Prevention and Mitigation
 
Prevention and mitigation include:
 
 
Closed Loop Therapy with meal gesture dosing will only be active during the in-clinic portion of study period. Subjects will be under constant surveillance by investigational center staff.
 
Follow the provided user guides for insulin pump management.
 
Train prior to study device use on appropriate device use and diabetes management principles and told to call with problems and instruct to call investigator with problems.
 
Instruct to check their meter glucose if their high or low symptoms do not match their sensor alerts or sensor glucose readings in order to make diabetes treatment decisions.
 
Instruct to check their meter glucose if there are any concerns that the sensor glucose value is not accurate.
 
Instruct if there are no sensor values, no treatments decision will be made until a BG is confirmed.
 
Instruct to have glucose on hand for hypoglycemia.
 
Instruct to avoid the use of products containing acetaminophen
 
If acetaminophen is taken, subjects will be instructed to use additional BG meter readings (they are not to calibrate with those readings) to verify their glucose levels.
 
If acetaminophen is taken, subjects will turn off Auto Correction and exit Auto Mode
 
Pump has cybersecurity encryptions to prevent hacking.
 
Instruct subjects to keep their own insulin pump supplies in a safe place and to have back up supplies in the event they are asked to revert back to their own therapy during the study
 


	

During the in-clinic portion of study period, subjects will be under constant surveillance by investigational center staff

Risks with hyperglycemia may include: 

Diabetic ketoacidosis

Symptomatic ketosis

Cardiovascular event

Dehydration

Potassium and sodium imbalance

Shock

Altered mental status

Coma

Acidosis

	Prevention and mitigation include: 

Closed Loop Therapy with meal gesture dosing will only be active during the in-clinic portion of study period. Subjects will be under constant surveillance by investigational center staff.

Follow the provided user guides for insulin pump management.

Train prior to study device use on appropriate device use and diabetes management principles and instruct to call investigator with problems.

Instruct to check their meter glucose if their high symptoms do not match their sensor alerts or sensor glucose readings in order to make diabetes treatment decisions.

Instruct to check their meter glucose if there are any concerns that the sensor glucose value is not accurate.

Instruct if there are no sensor values, no treatments decision will be made until a BG is confirmed.

Risks with hypoglycemia may include: 

Seizure

Coma

Altered mental status

Loss of consciousness

Cardiovascular event

Death

Risk of rebound hyperglycemia with ketosis

	Prevention and mitigation include: 

Closed Loop Therapy with meal gesture dosing will only be active during the in-clinic portion of study period. Subjects will be under constant surveillance by investigational center staff.

Follow the provided user guides for insulin pump management.

Train prior to study device use on appropriate device use and diabetes management principles and instruct to call investigator with problems.

Instruct to check their meter glucose if their low symptoms do not match their sensor alerts or sensor glucose readings in order to make diabetes treatment decisions.

Instruct to check their meter glucose if there are any concerns that the sensor glucose value is not accurate.

	
 
• Instruct if there are no sensor values, no treatment decisions will be made until a BG is confirmed
 
• Instruct to have glucose on hand for hypoglycemia
 

Risk with Acetaminophen Use	Prevention and Mitigation
Potential risks with acetaminophen may include: 
 
• False elevation of sensor glucose readings. The level of inaccuracy depends on the amount of acetaminophen active in subject's body and may be different for each subject
 
• Liver damage, liver failure and/or rare but fatal liver failure can occur
 
• Skin rash and/or serious and potentially fatal skin reactions have been reported
 
• Allergic reactions including those which are serious and potentially fatal can occur
 
• Kidney disease
 
• Lowered blood counts (red cells, and white cells)
 
	Prevention and mitigation include: 
 
• Follow the user guide
 
• Instruct to avoid the use of products containing acetaminophen
 
• If acetaminophen is taken, subjects will be instructed to use additional BG meter readings (they are not to calibrate with those readings) to verify their glucose levels
 
• If acetaminophen is taken while the SmartGuard feature is active, subjects will be instructed to use the temp target
 

## 11.2 Risk Minimization

Refer to "Prevention and Mitigation" column in the table under **Section 11.1**.

## 11.3 Potential Benefits

Subjects are not expected to benefit from participation in this study; however, they may gain increased awareness of emerging technologies for diabetes management as a result of their participation.

## 11.4 Risk-Benefit Rationale

Access to automated insulin devices during the trial may offer improved glycemic control for participants, and may increase understanding of the disorder, due to the fact that the participants will be followed with higher frequency of visits, which will allow a closer medical follow-up when compared to standard of care.

Furthermore, with any externally worn device there are small risks of insulin infusion site reactions, infection, and skin reactions to tapes – however it should be noted that this is no different to standard of care insulin pump therapy and utilizing continuous glucose monitoring.

In addition, any potential risks with this study are minimized by selecting qualified investigators experienced with insulin pump therapy, careful assessment of each subject during the study conduct to effectively monitor and rapidly remedy the problem. Furthermore, subjects can call the site to obtain technical support, if needed.

Medtronic has further minimized the possibility of risks by completing product testing prior to the use of the system in this clinical study, implementing quality control measures into production processes, providing guidelines for subject selection and evaluation, and providing adequate instructions and labelling according to local requirements.

All above these risks are contained within the patient information sheet, and indications and contraindications are provided in the Instructions for Use given to all patients.

## **12. Adverse Events and Device Deficiencies**

Throughout the course of the study, investigational centers will make all efforts to remain alert to possible reportable adverse events (AEs) or untoward findings. The study personnel will elicit reports of adverse events (AEs) from the subject at each visit (including phone calls) starting at the time of signing the informed consent documenting the medical diagnosis, date of event start and end, causality (relationship to device or procedure), treatment, outcome, and description that includes the details of the event.

### **12.1 Definitions and Classifications of Adverse Events and Device Deficiencies**

Medtronic uses the definitions provided in ISO 14155:2020 for AE definitions. Where the definition indicates "device", it refers to any device used in the study. This might be the device under investigation, or any market released component of the system.

**Severe Hypoglycemia** is an event requiring assistance of another person due to altered consciousness to actively administer carbohydrate, glucagon, or other resuscitative actions. This means that the subject was impaired cognitively to the point that he/she was unable to treat himself or herself, was unable to verbalize his or her needs, and was incoherent, disoriented and/or combative.

These episodes may be associated with sufficient neuroglycopenia to induce seizure or coma. Plasma glucose measurements may not be available during such an event, but neurological recovery attributable to the restoration of plasma glucose to normal is considered sufficient evidence that the event was induced by a low plasma glucose concentration.

**Severe Hyperglycemia** is defined as hyperglycemia (blood glucose greater than (>) 300 mg/dL or 16.7 mmol/L) with blood glucose ketones greater than (>) 1.5 mmol/L, and/or accompanied by symptoms of nausea, vomiting or abdominal pain.

The meter and ketone test strips are supplied for the evaluation of ketone monitoring. Only blood ketones will be recognized (not urine ketones) for assisting in diagnosis of severe hyperglycemia. The monitors/test strips are quality controlled prior to dispensing to subjects. Blood ketones provide contemporaneous understanding of ketone levels associated with elevations in glucose.

**Diabetic Ketoacidosis/DKA diagnostic criteria:** blood glucose greater than ( $> 250$  mg/dL or greater than ( $> 13.9$  mmol/L, arterial pH less than ( $< 7.3$ , bicarbonate less than ( $< 15$  mEq/L, moderate ketonuria or ketonemia and requiring treatment within a health care facility.

Hyperglycemic events will be recorded as DKA if the event includes the presence of all of the following:

- Arterial blood pH less than ( $< 7.30$  or serum bicarbonate less than ( $< 15$  mEq/L
- Blood glucose greater than ( $> 250$  mg/dL or greater than ( $> 13.9$  mmol/L
- Serum ketones or large/moderate urine ketones
- Symptoms such as polyuria, polydipsia, nausea, or vomiting
- Treatment provided in a health care facility

## Adverse Event (AE) (ISO 14155:2020)

Any untoward medical occurrence, unintended disease or injury, or untoward clinical signs (including abnormal laboratory findings) in subjects, users or other persons, whether or not related to the investigational medical device and whether anticipated or unanticipated.

**Note 1 to entry:** This definition includes events related to the investigational medical device or the comparator.

**Note 2 to entry:** This definition includes events related to the procedures involved.

**Note 3 to entry:** For users or other persons, this definition is restricted to events related to the use of investigational medical devices or comparators.

## Adverse Device Effect (ADE) (ISO 14155:2020)

Adverse event related to the use of an investigational medical device.

**Note 1 to entry:** This definition includes adverse events resulting from insufficient or inadequate instructions for use, deployment, implantation, installation, or operation, or any malfunction of the investigational medical device.

**Note 2 to entry:** This definition includes any event resulting from use error or from intentional misuse of the investigational medical device.

**Note 3 to entry:** This includes 'comparator' if the comparator is a medical device.

## Serious Adverse Event (SAE) (ISO 14155:2020)

Adverse event that led to any of the following

- a) death,

- b) serious deterioration in the health of the subject, users, or other persons as defined by one or more of the following:
  1. a life-threatening illness or injury, or
  2. a permanent impairment of a body structure or a body function including chronic diseases, or
  3. in-patient or prolonged hospitalization, or
  4. medical or surgical intervention to prevent life-threatening illness or injury or permanent impairment to a body structure or a body function,
- c) fetal distress, fetal death or a congenital abnormality or birth defect including physical or mental impairment

**Note 1 to entry:** Planned hospitalization for a pre-existing condition, or a procedure required by the CIP, without serious deterioration in health, is not considered a serious adverse event.

### **Serious Adverse Device Effect (SADE) (ISO 14155:2020)**

Adverse device effect that has resulted in any of the consequences characteristic of a serious adverse event

### **Unanticipated Serious Adverse Device Effect (USADE) (ISO 14155:2020)**

Serious adverse device effect which by its nature, incidence, severity or outcome has not been identified in the current risk assessment.

**Note 1:** Anticipated serious adverse device effect (ASADE) is an effect which by its nature, incidence, severity or outcome has been identified in the risk assessment.

### **Serious Health Threat (ISO 14155:2020)**

Signal from any adverse event or device deficiency that indicates an imminent risk of death or a serious deterioration in the health in subjects, users or other persons, and that requires prompt remedial action for other subjects, users or other persons

Note 1 to entry: This would include events that are of significant and unexpected nature such that they become alarming as a potential serious health hazard or possibility of multiple deaths occurring at short intervals.

### **Device Deficiency (ISO 14155:2020)**

A device deficiency is any inadequacy of a medical device with respect to its identity, quality, durability, reliability, safety, or performance.

**Note 1:** Device deficiencies include malfunctions, use errors, and inadequacy in the information supplied by the manufacturer including labelling.

**Note 2:** This definition includes device deficiencies related to the investigational medical device or the comparator.

## 12.2 Reporting of Adverse Events and Device Deficiencies

The investigator or designee will record all AEs and DDs while the subject is enrolled in the clinical study.

Each AE needs to be assessed for its device or procedure relatedness. A device related AE is associated with the use of the study device (e.g. infection of sensor site or infusion set occlusion resulting in DKA). A procedure related AE is associated with testing related to the study procedures specified in the CIP.

Examples of device or procedure related AEs include:

- **Device** related: insertion site infection
- Serious adverse **device effect**: cellulitis at device insertion site requiring hospitalization
- **Procedure** related AE: meal challenge procedure

Subjects participating in the study have diabetes and are expected to experience hypoglycemia and or hyperglycemia. These normal events are not expected to be reported to sponsor on an AE eCRF as this is not considered an untoward event, but rather an expected occurrence. Any glycemic excursion that meets the protocol definition of Severe Hypoglycemia, Severe Hyperglycemia or DKA is considered an untoward event and a worsening from the subject's baseline and would be reported to sponsor on an AE eCRF.

Baseline medical conditions should only be reported to sponsor on an AE eCRF, if there is a worsening from the subject's baseline. For example, a subject previously diagnosed with Asthma is hospitalized for severe asthma attack would be a reportable event.

Adverse events will be documented in the subject source file and reported to sponsor on an eCRF. The investigational center is responsible for documentation of AEs including obtaining source documents related to the event, such as emergency medical technician/paramedic reports, hospital records (admission summary; lab results, test results, discharge summary) or device uploads to support the event. Source documents will be reviewed to determine if additional AEs have occurred and require reporting.

Adverse events that have not resolved at the time of the subject's discontinuation or completion of the study should have an "outcome" of Not Recovered/Not Resolved at study end in subject source and on an eCRF. The investigator should ensure that subject is aware of any follow-up or additional treatment that is required for any ongoing AE at end of study participation; however, there will be no eCRF entry for the ongoing follow-up.

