## **10.12 Assessment of Safety**

All AE information is collected in this study. See **Section 12** for further information on the collection of AEs and safety information.

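### Section 12.2 states no exception for device-caused hypo- or hyperglycemia short of the severe definitions, so the ADE count omits such events

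*Protocol*

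**What the plan says.** Protocol Section 12.2 notes that participants are expected to have low and high glucose and says: "These normal events are not expected to be reported to sponsor on an AE eCRF as this is not considered an untoward event". It then names what is reportable: "Any glycemic excursion that meets the protocol definition of Severe Hypoglycemia, Severe Hyperglycemia or DKA is considered an untoward event". Severe hypoglycemia, under Section 12.1, "is an event requiring assistance of another person due to altered consciousness to actively administer carbohydrate, glucagon, or other resuscitative actions"; it has no glucose threshold.

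Other parts of the protocol read more widely:

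- The AE definition in Section 12.1 applies "whether or not related to the investigational medical device and whether anticipated or unanticipated".
- The ADE definition there covers AEs related to the use of an investigational device, including those from use error "or any malfunction of the investigational medical device".
- Section 10.12 states: "All AE information is collected in this study".
- Section 11.1, Table 5, says the risks of closed loop "with meal gesture dosing are related to the potential for delivery of too much or too little insulin which can result in" a list of harms. Plain hypoglycemia and plain hyperglycemia stand in that list as separate entries from severe hypoglycemia and DKA.
- Table 4 in Section 10.4 tells staff to record on the eCRF a deterioration of an existing condition, and gives glycemic problems as an example.

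The safety endpoints (protocol 5.2.2 and 14.5.2, SAP 7.9.2) are counts of (S)AEs, (S)ADEs, USADEs, severe hypoglycemic events, DKA events and device deficiencies. Sensor-based low and high glucose measures are Other Endpoints (protocol 14.5.3, SAP 7.9.3).

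**The concern.** The stated purpose of the study is to evaluate the safety of gesture dosing, and Table 5 traces its risk to over- or under-delivery of insulin. The most direct sign of mis-dosing is a low or high glucose, which in most cases can be treated before it becomes severe. Section 12.2 exempts such excursions because people with diabetes have them anyway. That reasoning does not fit a low that follows an automatic announcement when no carbohydrate was eaten.

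At stake is whether the ADE count can be read as the investigator's account of harm from the device. If 12.2 is followed as written, repeated, treated, non-severe lows that the investigator blames on gesture dosing would add nothing to that count. In addition, 12.2 and Table 4 could lead two members of staff to record the same event differently.

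**Working it through.** The plan gives no figure to reproduce on this point. The check sets the passages side by side and follows one hypothetical event through them.

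**Test case.** On Day 3 in clinic the subject takes the large no-carbohydrate drink (10.1 and 10.3.2.1.3). The app detects drinking as well as eating gestures (7.1.1.3). Suppose that it sends an announcement, sensor glucose falls below 54 mg/dL, and the subject, still alert, takes oral carbohydrate and recovers.

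1. *Severe hypoglycemia (12.1)?* No. The definition needs assistance because of altered consciousness. Gesture dosing is active only in clinic under constant surveillance (Table 5), so a low is likely to be treated before that point.
2. *AE (12.2)?* No. It meets none of the three named definitions, and no exception for device causation is stated.
3. *ADE (12.1)?* No. An ADE is by definition an AE, so step 2 closes this route. The causality grading in 12.4 applies to AEs and is not reached.
4. *Device deficiency (12.5)?* Possibly, if staff recognise a fault. But 12.5 sends to the deficiency form those faults that led to no AE. Since 12.2 says there was no AE, the fault may be filed without its link to the low.
5. *CEC (13.1)?* Not among the listed event types, which are serious events, severe hypoglycemia, DKA and deaths.
6. *Sensor endpoints (14.5.3, SAP 7.9.3)?* Yes. The low is counted, by period, but with no causality assessment and not as a safety endpoint.
7. *Table 4?* It points the other way from step 2, because it names glycemic problems among the deteriorations to record.

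**Serious excursions.** One SAE criterion is "medical or surgical intervention to prevent life-threatening illness or injury or permanent impairment to a body structure or a body function". An excursion could meet it, or lead to hospitalization, without altered consciousness. Section 12.2 does not address that case. Table 6 and Section 12.3 require SAEs to be reported and exclude no glycemic event. Section 12.2 itself makes worsening from baseline reportable, with a hospitalization as its example. This is a gap in 12.2, not an exclusion.

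**Size.** Nominal gesture-dosing exposure, one stay each, is 16 × 5 = 80 subject-days for the minimum number of completers and 40 × 5 = 200 if all 40 were dosed. The number of events missed is exposure × the rate of device-attributed sub-severe excursions. The documents give no such rate, so no number follows.

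The sample size does show how little a zero count of any one severe event type can exclude. The one-sided 95% upper limit on per-subject risk with no events is 1 − 0.05^(1/n):

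- n = 16: 1 − 0.05^(1/16) = 17.1%
- n = 40: 1 − 0.05^(1/40) = 7.2%

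These limits describe the severe-event counts. They do not measure the undercount.

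**The case against.** The case on the other side has five parts.

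- *The AE definition.* It begins with untoward occurrences, and the phrase about anticipated events qualifies those. Section 12.2 classes ordinary excursions as not untoward, and Table 5 is a risk list that sets no reporting rule. This stands in part: the passages are in tension and are not a flat contradiction. The tension with Table 4 is plainer, because both passages govern what goes on the eCRF.
- *Serious events.* A reader might infer that 12.2 keeps an excursion off the AE form even when it is serious. The text does not support that. The exemption speaks of normal events, and the SAE definition, Table 6 and the worsening rule point towards reporting.
- *Other routes into the safety counts.* A reader might infer that the safety endpoints cannot contain the device's likely harm. They can in part. Severe hypoglycemia, severe hyperglycemia and DKA reach the AE form, and 12.4 works through device causality for a severe hyperglycemia AE. Faults reach the deficiency count and are assessed for SADE potential.
- *Sensor data.* Lows and highs are measured within subject, by period and meal type, and postprandial insulin delivery is analysed too. This stands. What is missing is investigator attribution and a place among the safety results.
- *Event rates.* A reader might infer that the glycemic ADE count will be near zero whatever the device does. That needs assumed rates, and an argument from severe hypoglycemia alone leaves out severe hyperglycemia and DKA.

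None of this supplies the missing exception for device causation.

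**Conclusion.** The concern holds in a limited form. As written, Section 12.2 lets a glycemic event count as an ADE only when it meets one of the three severe definitions. Sub-severe lows or highs attributed to gesture dosing fall outside the ADE endpoint and appear only as unattributed sensor measures. Section 12.2 is also silent on serious excursions and does not agree with Table 4. The safety endpoints are therefore incomplete, though not empty.

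The conclusion rests on staff following 12.2 as written; staff who follow Table 4 instead may record some of these events. The size of the undercount cannot be derived from the documents. The change is worth making because safety is the stated purpose and the correction is short.

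**What to change.** **Protocol 12.2.** Reconcile it with 12.1 and Table 4 by adding a statement such as: the exemption does not cover a glycemic excursion that the investigator judges related to a study device or its dosing under the 12.4 categories, or one that meets any SAE criterion in 12.1; these are recorded on the AE eCRF with their 12.4 category. Word the Table 4 instruction to match.

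**SAP 7.9.2.** Show the ADE count with and without sub-severe glycemic ADEs, split into possible, probable and causal. Admitting only probable or causal cases would set a stricter threshold for glycemic ADEs than for other ADEs; the split avoids this and still lets a reader set aside weak attributions. Show in-clinic SG events below 54 and 70 mg/dL beside the safety endpoints.

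**Cost.** A short addition to 12.2, a matching edit to Table 4 and added rows in the safety table. The downside is some extra AE forms and a less favourable ADE count. This changes reporting only and leaves the treatment of excursions as it is.

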#### **10.3.2.1.6 End of Study**

- Collect all study devices back from subject
- End of study

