## **10.8 End of Study Visit**

After the study has been completed (at Visit 7 or in case of early termination), the subjects will complete their end of study visit. The subjects will continue to be treated following the routine practice of each center.

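### No planned route captures adverse events that worsen or first appear after device return, so a late upgrade to serious can be missing from the SAE and SADE counts

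*Protocol*

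**What the plan says.** **Recording window.** Protocol Section 12 has staff elicit events at every visit and phone call, "starting at the time of signing the informed consent". Section 12.2 sets the limit: "The investigator or designee will record all AEs and DDs while the subject is enrolled in the clinical study". The SAP (7.2) covers data from screening to the end of the study, and its safety endpoints (7.9.2, 7.10) are event counts with no observation window after exit.

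**Events open at exit.** Section 12.2 gives them the outcome "Not Recovered/Not Resolved at study end in subject source and on an eCRF". The investigator makes sure the subject knows what further care is needed, but "there will be no eCRF entry for the ongoing follow-up".

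**Timing of exit.** Table 5 (Section 11.1) states: "Closed Loop Therapy with meal gesture dosing will only be active during the in-clinic portion of study period". That stay is Visit 7. The End of Study entry (10.3.2.1.6) follows Day 5 directly and begins "Collect all study devices back from subject". Section 10.8 adds: "After the study has been completed (at Visit 7 or in case of early termination), the subjects will complete their end of study visit". Table 4 places the last AE question, the last device question and device collection in one End of Study column, for which no day or window is visible. Sections 10.8 and 10.15 return the subject to routine care, with no later study contact.

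**Serious events.** Table 6 has the site report SAEs, SADEs and USADEs to the sponsor within 24 hours of first awareness and states no cut-off at subject exit. Section 12.3 makes the completed AE eCRF the means of notification, with e-mail as the fallback when the database cannot be reached.

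**The concern.** The stated purpose is to evaluate subject safety in a clinic setting, and gesture dosing runs only in the last phase before exit. Followed exactly, the plan fixes the seriousness and outcome of every open event when the subject leaves.

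The protocol's own examples in 12.2 show what could be missed. It gives an insertion site infection as a device-related event, and "cellulitis at device insertion site requiring hospitalization" as a serious adverse device effect. If the infection is open at exit and the admission comes days later, the record stays a non-serious device event. A site reaction that first shows after the last visit is not solicited at all.

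At stake are the completeness of the SAE, SADE and USADE counts and the outcomes available to the sponsor and the Clinical Events Committee. The committee's adjudication is used for analysis (13.1), but it can review only what is reported. Subjects may also repeat participation (Section 6), so an unrecorded outcome could matter when re-exposure is considered.

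**Working it through.** The documents give no figure for the safety window, so there is nothing to reproduce. The check follows four kinds of event through the written rules.

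| Event | What the plan does with it |
|---|---|
| Starts, and resolves or turns serious, before exit | Fully recorded. This covers the run-in (about 1 week to 3 months), the at-home period and the clinic stay. |
| Open at exit, no later change in seriousness | Stays in the counts as classified at exit. The final outcome is not entered (12.2). |
| Open at exit, becomes serious afterwards | Stays in the counts as non-serious. The upgrade belongs to the later course, for which 12.2 allows no eCRF entry. |
| Device-site event that first appears after exit | No contact asks about it, and it falls outside the enrolled period in 12.2. |

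**Does Table 6 close the last two rows?** Not as written.

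1. Its 24-hour clock starts at site awareness, and no planned contact after exit creates that awareness.
2. If the site does learn of the event, 12.3 sends the report through the AE eCRF. For an event open at exit, 12.2 excludes that entry.
3. The sentence below Table 6 limits the sponsor's onward reporting to events occurring during the study.
4. Neither document says whether such a report would enter the endpoint counts. The enrolled-period wording in 12.2 and the end-of-study wording in SAP 7.2 point against it.

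**When is exit?** The synopsis gives a minimum of 7 planned visits and Section 10.1 a minimum of 8. A repeated meal challenge may add a day. The end-of-study visit could therefore be the last clinic day or a separate contact.

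**Scale, for illustration only.** The share m of device-related serious events that fall after exit is not in the documents. I assume 0, 25% and 50%. The numbers of subjects are the plan's own: at least 16 completers and up to 40 enrolled.

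With zero events observed in n subjects, the one-sided 95% upper bound on the observable per-subject rate is 1 − 0.05^(1/n). If only a fraction 1 − m is observable, the bound on the true rate is that value divided by 1 − m.

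- n = 16: 1 − 0.05^(1/16) = 17.1%. With m = 25%, 0.1707/0.75 = 22.8%. With m = 50%, 0.1707/0.50 = 34.1%.
- n = 40: 1 − 0.05^(1/40) = 7.2%. With m = 25%, 0.0722/0.75 = 9.6%. With m = 50%, 0.0722/0.50 = 14.4%.

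The chance of seeing at least one event is 1 − (1 − p(1 − m))^n. At an assumed true rate p = 5%:

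- n = 16: 56.0% (m = 0), 45.7% (m = 25%), 33.3% (m = 50%).
- n = 40: 87.1%, 78.3%, 63.7%.

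**The case against.** **Stronger readings that a reader might infer.** Three go further than the text.

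- *Recording stops on the day gesture dosing ends.* The cut-off in 12.2 is the end of enrollment, and the day of the end-of-study visit is not stated.
- *Removal of the last sensor goes unobserved.* The transmitter connected to the sensor must be returned, and Table 4 puts device collection and an AE question in the same column. A reaction visible at that contact can be recorded.
- *Late serious events can never reach the sponsor.* Table 6 states no exit cut-off, and open events are not dropped from the counts. What is missing is a planned route for their later course.

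**The case for leaving the plan alone.** This is an unpowered feasibility study, the purpose is limited to the clinic setting, and the cut-off is openly declared. The risk that Table 5 assigns to gesture dosing is too much or too little insulin, which is addressed by constant surveillance in the clinic. The examples above are skin events from CE-marked sensors and infusion sets, whose skin risks Section 11.4 regards as no different from standard pump care. Earlier sites are followed by AE questions at later visits, so only the last sites lack a tail. After exit subjects return to routine treatment, so a late site event may come from their own devices.

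**What of it stands.** The gap is a tail, attribution within it is harder, and it mainly concerns events not specific to gesture dosing. But 12.1 counts any device used in the study, including marketed components, and the safety endpoints do the same. Difficult attribution is a matter for the causality assessment in 12.4. It does not justify fixing seriousness at exit. Advising the subject about further care protects the subject but collects no data.

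**Conclusion.** The point holds in a limited form. No safety contact is scheduled after device return at the end-of-study visit, and 12.2 rules out eCRF entry for the later course of events open at exit. Those events remain counted as classified at exit. Their outcome and any later upgrade to serious have no planned route into the SAE and SADE counts, and device-site events that first appear after the last visit are not solicited. For a serious event learned of after exit, the text of 12.2, Table 6 and 12.3 need reconciling.

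The effect on the serious counts can only be downward. Its size cannot be estimated, because the documents give neither an event rate nor a share falling after exit. The percentages above rest on assumed values and show only that, with 16 to 40 subjects, a missed share of that order would weaken a finding of no events. Event capture before exit is not called into question. The plan should be changed because the remedy is small and the present rule would leave a known upgrade out of the record.

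**What to change.** 1. In Protocol 12.2, replace the clause that excludes eCRF entry. SAEs, device- or procedure-related AEs, severe hypoglycemia, severe hyperglycemia and DKA ongoing at exit are followed to resolution, stabilisation or database lock. The outcome and any change in seriousness go on the same AE eCRF.
2. State the day of the end-of-study visit and the end of the AE recording window, and carry that window into SAP 7.9.2 and 7.10.
3. Reconcile 12.2 with Table 6 and 12.3 for serious events learned of after exit: how they are entered and whether they count toward the endpoints.
4. Optionally, add one AE and device phone contact after device return, made by existing site staff in the manner of Visits 3 to 6, with the recording window extended to it.

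The cost is protocol and consent wording, some AE records kept open longer, and one call per subject if item 4 is adopted. The downsides are slightly later data cleaning, possibly a few more reported events, and some post-exit events that are hard to attribute once subjects are back on their own devices.
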